## **5. INVESTIGATIONAL PRODUCT(S)**

### **5.1 MEDI4736**

The Investigational Products Supply section of AstraZeneca/MedImmune will supply MEDI4736 to the investigator as a concentrate for solution for infusion.

#### **5.1.1 Formulation/packaging/storage**

MEDI4736 is formulated at 50 mg/mL in 26 mM histidine/histidine-HCl, 275 mM trehalose dihydrate, 0.02% (w/v) polysorbate 80, pH 6.0.

The investigational product is supplied as a vialed liquid solution in clear 10R glass vials closed with an elastomeric stopper and a flip-off cap over seal. Each vial contains 500 mg (nominal) of active investigational product at a concentration of 50 mg/mL (500 mg/vial). The solution will be diluted with 0.9% (w/v) saline for IV infusion.

Unopened vials of liquid MEDI4736 must be stored at 2°C to 8°C (36°F to 46°F). MEDI4736 must be used within the individually assigned expiry date on the label.

## **In use storage and stability**

Total in-use storage time from needle puncture of MEDI4736 vial to start of administration should not exceed 4 hours at room temperature or 24 hours at 2-8°C (36-46°F). If in-use storage time exceeds these limits, a new dose must be prepared from new vials. Infusion solutions must be allowed to equilibrate to room temperature prior to commencement of administration. MEDI4736 does not contain preservatives and any unused portion must be discarded.

### **5.1.2 Doses and treatment regimens**

Subjects will be administered a 15 mg/kg intravenous dose of MEDI4736 once during the study.

### **5.1.3 Study drug preparation**

Calculate the dose volume of MEDI4736 and number of vials needed for the subject to achieve the accurate dose according to Appendix A.

### **Preparation of infusion bags**

The preparation of infusion bags should be done under aseptic conditions by trained personnel; it should **not** be prepared on the ward.

An additional volume of 0.9% (w/v) saline equal to the calculated volume of MEDI4736 to be added to the IV bag must be removed from the bag prior to addition of MEDI4736.

The calculated volume of MEDI4736 is then added to the IV bag, and the bag is mixed by gentle inversion to ensure homogeneity of the dose in the bag.

Prior to the start of the infusion, ensure that the bag contents are at room temperature to avoid an infusion reaction due to the administration of the solution at low temperatures.

Vials should be used for specific subjects and should not be shared between subjects.

### **5.1.4 Dose administration**

MEDI4736 will be administered at room temperature (approximately 25°C ) by controlled infusion via an infusion pump into a peripheral vein.

Clinical Study Protocol

Drug Substance Tremelimumab

Study Number **ESR-14-10744**

Edition Number 8

Date 17 April 2019

Following preparation of MEDI4736, the entire contents of the IV bag should be administered as an IV infusion over approximately 60 minutes ( $\pm 5$  minutes), using a 0.2- $\mu$ m in-line filter.

The IV line will be flushed with a volume of normal saline equal to the priming volume of the infusion set used after the contents of the IV bag are fully administered, or complete the infusion according to institutional policy to ensure the full dose is administered and document if the line was not flushed.

Since the compatibility of MEDI4736 with other IV medications and solutions, other than normal saline (0.9% [weight/volume] sodium chloride for injection), is not known, the MEDI4736 solution should not be infused through an IV line in which other solutions or medications are being administered.

### **5.1.5 Monitoring of dose administration**

Subjects will be monitored during and after the infusion with assessment of vital signs at the times specified in the Schedule of Assessment (see Section 6.2)

In the event of a  $\leq$ Grade 2 infusion-related reaction, the infusion rate of study drug may be decreased by 50% or interrupted until resolution of the event (up to 4 hours) and re-initiated at 50% of the initial rate until completion of the infusion. For subjects with a  $\leq$ Grade 2 infusion-related reaction, subsequent infusions may be administered at 50% of the initial rate. Acetaminophen and/or an antihistamine (e.g., diphenhydramine) or equivalent medications per institutional standard may be administered at the discretion of the investigator. If the infusion-related reaction is  $\geq$ Grade 3 or higher in severity, study drug will be discontinued.

As with any antibody, allergic reactions to dose administration are possible. Appropriate drugs and medical equipment to treat acute anaphylactic reactions must be immediately available, and study personnel must be trained to recognize and treat anaphylaxis. The study site must have immediate access to emergency resuscitation teams and equipment in addition to the ability to admit subjects to an intensive care unit if necessary.

### **5.1.6 Accountability and dispensation**

The investigator will assure that drug accountability records will maintain a current disposition of all investigational drugs, including their inventory and dispensing. Our records will comply with applicable regulations and guidelines that include:

1. Amount received and placed in storage;
2. Label ID number or batch number;
3. Amount dispensed, including unique subject identifiers;
4. Amount, if applicable, transferred from one area to another for dispensing or storage;
5. Non-study disposition (i.e., lost or unused);
6. Amount destroyed, if applicable;
7. Dates and initials of person responsible for Investigational Product (IP) dispensing/accountability, as per the Delegation of Responsibility Form.

**5.1.7** Disposition of unused investigational study drug. At the completion of the study, all unused MEDI4736 will be returned to the sponsor

## **5.2 Tremelimumab**

The Investigational Products Supply section of AstraZeneca/MedImmune will supply tremelimumab to the investigator as a concentrate for solution for infusion.

### **5.2.1 Formulation/packaging/storage**

Tremelimumab Drug Product is formulated at a nominal concentration of 20 mg/mL in 20 mM histidine/histidine hydrochloride, 222 mM trehalose dihydrate, 0.02% (weight/volume [w/v]) polysorbate 80, 0.27 mM disodium edetate dihydrate (EDTA), pH 5.5.

The Drug Product is supplied as a sterile IV solution in 20 mL clear glass vials with a rubber stopper and aluminum seal. Each vial contains 20 mg/mL of tremelimumab with a nominal fill of 20 mL (accounting to 400 mg/vial). Vials containing tremelimumab must be stored at 2°C to 8°C (36°F to 46°F) and must not be frozen. Tremelimumab is administered as an IV infusion after dilution in sterile, normal saline for injection. The product should be protected from light when not in use.

### **5.2.2 Doses and treatment regimens**

Subjects will be administered MEDI4736 (1500 mg intravenously) + tremelimumab (75 mg intravenously) once during the study.

Subjects under 30 kg will be treated with weight-based dosing for both MEDI4736 and Tremelimumab combination therapy. These patients are excluded from fixed based dosing to limit endotoxin exposure from the drug preparations.

### **5.2.3 Product preparation**

MEDI4736 + tremelimumab will be prepared following the procedures outlined in Section 5.1.3.

### **5.2.4 Dose administration**

MEDI4736 + tremelimumab will be administered following the procedures outlined in Section 5.1.3.

### **5.2.5 Monitoring of dose administration**

Subjects receiving MEDI4736 + tremelimumab will be monitored during and after the infusion following the procedures outlined in Section 5.2.5.

### **5.2.6 Accountability and dispensation**

Drug accountability records will be kept as described in Section 5.1.6.

### **5.2.7 Disposition of unused investigational study drug**

At the completion of the study, all unused MEDI4736 and Tremelimumab will be destroyed at the study site with proper documentation.

## **TREATMENT PLAN**

### **5.3 Subject enrollment and randomization**

We expect to enroll a total of 20 evaluable subjects (if tissue obtained at time of thoracoscopy and time of surgical resection) with surgically resectable MPM to this study over a period of 24 months. Subjects will be randomized. Subjects will be assigned to one of the three treatments (n = 8 MEDI4736, n = 8 MEDI4736 + tremelimumab, and n=4 control). All subjects will undergo surgical resection one to six weeks after the infusion.

#### **5.3.1 Procedures for randomization**

After mediastinoscopy + thoracoscopy, eligible subjects with MPM will be randomized in 2:2:1 ratio to one of three arms: MEDI4736 alone, MEDI4736 + tremelimumab, and a control group of neither MEDI4736 nor tremelimumab. A computer-generated randomization scheme may be generated by the Biostatistics Core, Baylor College of Medicine. Randomization will be accomplished via access to a secure website developed by the Biostatistics Core and automatically notified to the study coordinator or the investigator via email. Randomization will be stratified by receiving previous chemotherapy or not.

### **5.3.2 Procedures for handling subjects incorrectly enrolled or randomized**

Subjects who are incorrectly enrolled in the study but have not yet received treatment with MEDI4736 or MEDI4736 + tremelimumab will be withdrawn from the study and will receive standard of care treatment for their MPM.

Subjects who are found to have been incorrectly enrolled after receiving treatment will be withdrawn from the study and will receive standard of care treatment for their MPM. Such patients will be replaced by eligible subjects with MPM. These subjects also will be followed for 90 days to track any AEs, SAEs, etc. from the treatment. These subjects will not be included in any data analyses.

## **5.4 Blinding and procedures for unblinding the study**

### **5.4.1 Methods for ensuring blinding**

This is an open-label study design; both investigators and subjects will know which study drug the subject is receiving.

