### **Efficacy Assessments:**

#### **PRIMARY ENDPOINTS**

- 1) Intratumoral CD8/Treg ratio determined by CyTOF.

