### **5.4.2 Methods for unblinding the study**

Not applicable.

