#### **7.3.1 Biomarker/Pharmacodynamic sampling and evaluation methods**

Tissue biomarker immune response to MEDI4736 or MEDI4736 + tremelimumab will be determined on tissue and blood collected before and after the administration of the study drug(s), or in patients not receiving study drugs. The tissue biomarker immune responses that will be evaluated in this study include CD8/Treg ratios, percentage of ICOS+ CD4 T cells, and immune cell expression of PD-L1. CD8/Treg ratios and percentage of ICOS+ CD4 T cells will be compared with CyTOF (time-of-flight mass cytometry) and/or flow cytometry. Tumor PD-L1 expression will be determined by immunohistochemistry. CyTOF and/or flow cytometry will be used to compare PD-L1 expression on specific immune cell and non-immune cell populations.

Bone marrow biomarker immune response will also be assessed. Bone marrow will be collected from a routinely resected sixth rib during the surgical resection scheduled post-treatment with MEDI4736 or MEDI4736 + tremelimumab, or in patients not receiving study drugs. A comprehensive evaluation of immune cell composition and phenotype with CyTOF will be conducted on bone marrow tissue as well as tumor tissue and peripheral blood. Appendix C details the complete CyTOF panel that will be used for each individual specimen.

Clinical Study Protocol

Drug Substance Tremelimumab

Study Number **ESR-14-10744**

Edition Number 8

Date 17 April 2019

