## **8. DISEASE EVALUATION AND METHODS**

### **8.1.1 Primary Efficacy Variables**

1) The primary objective of this study will be comparison of the ratio of intratumoral cytotoxic T cells to regulatory T cells (CD8/Treg) before and after treatment with combination MEDI-4736 and Tremelimumab checkpoint inhibitor therapy. CD8/Treg ratios will be determined with CyTOF

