## APPENDIX C: CyTOF Antibody Panel including cell definitions

Cell Type	Definition	Subset or Activation Markers
Viability	Cisplatin-	
Immune cell	CD45+	
T cell	CD3+	CD4, CD8, FoxP3, CD25, CD127, CD45RA, CD62L, ICOS, CCR4, CCR6, Tim1
Dendritic cells	HLA-DR+, CD3-, CD14-, CD19-, CD56-	BDCA-1, BDCA-2, BDCA-3, BDCA-4, CD16
MDSC	CD11b+, CD15+	
Macrophage	CD68+	CD163, CD206
Monocyte	CD14+	CD16
B	CD19+	HLA-DR, CD27, CD38
NK	CD56+, CD3-	CD314, CD69
NKT	V224+, Vbeta11+	
PMN	SSC hi, CD15+	CD66b
RBC	CD235a/b	
Platelet	CD61+	
Tumor cell	CD45-	
All cells		PD-1, PD-L1, CTLA-4
All myeloid cells		HLA-DR, CD40, CD80, CD86, ICOSL
T cell polarization		interferon-gamma, TNF-alpha, IL-17, IL-2
Other		Ki-67

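### Masked laboratory reading is not specified, one sentence reopens the platform for the primary ratio, and the Treg gate is not defined, so a reading difference between time points would enter the primary result directly

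*Combined protocol and SAP*

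**What the plan says.** **Masking.** Section 5.4.1: "This is an open-label study design; both investigators and subjects will know which study drug the subject is receiving". Section 5.4.2, on unblinding, says only "Not applicable". Under 5.3.1 the allocation is "automatically notified to the study coordinator or the investigator via email". The sections on study design, sampling, assays, efficacy variables, analysis and training (3.1, 7.3, 8.1, 10.3, 12.1) say nothing about what the cytometry or PD-L1 reader may know. Section 13 assigns a subject number for confidentiality, but does not say that it hides arm or time point.

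**Platform.** The synopsis defines the primary endpoint as "Intratumoral CD8/Treg ratio determined by CyTOF", and 8.1.1 says "CD8/Treg ratios will be determined with CyTOF". The study-design text in the synopsis and in 3.1 also names CyTOF for this ratio. Section 7.3.1 reads differently: "CD8/Treg ratios and percentage of ICOS+ CD4 T cells will be compared with CyTOF (time-of-flight mass cytometry) and/or flow cytometry".

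**Gate.** The T-cell row of Appendix C lists "CD4, CD8, FoxP3, CD25, CD127, CD45RA, CD62L, ICOS, CCR4, CCR6, Tim1" together as subset or activation markers. The appendix has no Treg row. The synopsis (Secondary Endpoints, item 5a) and section 8.1.2 (item 8a) place FoxP3 with CD4 and CD8 as subset markers, and CD25 and CD127 with the memory and activation phenotype.

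**PD-L1.** Section 7.3.1: "Tumor PD-L1 expression will be determined by immunohistochemistry". The Ventana assay is named, but no scoring rule or reader procedure is given.

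**Primary test.** Section 10.3 specifies a paired t-test on the log ratio, before against after, in the combination arm only. That arm has 8 patients.

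**The concern.** CD8/Treg by cytometry depends on where gates are drawn, and PD-L1 by immunohistochemistry depends on how staining is scored. Both leave room for judgement. Open-label treatment does not require open-label reading, and here reading can be masked at little cost.

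The design gives the primary result little protection. It is a within-patient change in one arm, so randomisation does not guard it and the four controls do not enter it. If post-treatment samples are gated differently from baseline samples, measured on a different platform, or analysed in several ways with one chosen after the results are seen, the difference is counted as a treatment effect. As written, 7.3.1 permits a platform mismatch within a pair and a choice between platforms after the fact. The PD-L1 part of the point touches secondary endpoints only.

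**Working it through.** **Inputs** (sample-size text in section 10 and the synopsis): 8 pairs; log-scale baseline mean 1.94; SD 0.808 from 6 pilot subjects; within-pair correlation r = 0.5; detectable post-treatment mean 2.87; alpha 5%; power 80%. Sidedness is not stated.

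**1. The plan's own figure.**
- SD of the difference = 0.808 × √(2(1 − 0.5)) = 0.808.
- Difference = 2.87 − 1.94 = 0.93, and exp(0.93) = 2.53-fold.
- Noncentrality = 0.93/0.808 × √8 = 3.26, with 7 degrees of freedom.
- Power from the noncentral t is 79.7% two-sided and 89.9% one-sided.

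The two-sided test reproduces the stated 80%. At exactly 80% power the detectable difference is 0.934, and exp(1.94 + 0.934) = 17.71, the plan's raw-scale value. The sample-size arithmetic is sound on its own inputs.

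**2. What reaches significance.** With an observed SD of 0.808, p = 0.05 needs a mean change of 2.365 × 0.808/√8 = 0.676, which is exp(0.676) = 1.97-fold.

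**3. Effect of a differential reading shift.** Suppose the drugs do nothing, but post-treatment samples read higher than baseline samples by an average factor f. The rejection rate is then the power of the same test at noncentrality ln(f)/0.808 × √8. The documents give no value for f; every value below is an assumption.

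| Assumed shift f | ln(f) | Noncentrality | Two-sided rejection rate |
|---|---|---|---|
| 1.0 | 0 | 0 | 5.0% |
| 1.1 | 0.095 | 0.33 | 6.0% |
| 1.2 | 0.182 | 0.64 | 8.6% |
| 1.3 | 0.262 | 0.92 | 12.6% |
| 1.5 | 0.405 | 1.42 | 23.3% |

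The result also depends on the assumed correlation. For a 1.5-fold shift, r = 0.25 (SD of difference 0.990) gives 17.2%, and r = 0.75 (SD 0.571) gives 41.0%.

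**4. Choosing between two platforms.** Suppose there is no shift, but both CyTOF and flow cytometry are run and the result counts as positive if either reaches p < 0.05. By simulation, the false-positive rate is about 9.2% if the two analyses correlate at 0.5, and 7.4% if they correlate at 0.9. These correlations are also assumptions.

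**5. When there is no bias.** A gate applied identically to both samples of a pair corresponds to f = 1 in step 3 as far as gating is concerned. The inflation arises only when reading differs by time point or an analysis is selected after results are seen.

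**The case against.** The case against is substantial, and most of it limits the point.

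- **Readers.** One might infer from 5.4.1 that readers are unmasked by design. The sentence covers investigators and subjects only. The supportable statement is that reader masking is not specified.
- **Platform.** One might infer that the platform is simply open. It is not: the endpoint definition, 8.1.1 and both study-design texts name CyTOF, and the synopsis tissue-priority list puts CyTOF first without mentioning flow cytometry. A single sentence in 7.3.1 conflicts with them. It still has to be reconciled, because it is the sentence in the methods section.
- **Gate.** One might infer that any mix of FoxP3, CD25 and CD127 could serve. The synopsis and 8.1.2 point to FoxP3 as the subset marker. What is missing is an explicit Treg definition and gate.
- **Size.** No passage supports any particular reading shift. The figures say nothing about ICOS or PD-L1.
- **Controls.** There is a randomised untreated arm, and a drift common to all arms could show there. But it has four patients, sits outside the primary test, and would not reveal a drift specific to post-combination samples. Baseline tissue is taken before randomisation, so a prompt baseline read would be masked to arm; the documents do not say when reading takes place.
- **Feasibility.** A biopsy of about 2 g and a resection of 200–1000 g are easy to tell apart for anyone handling tissue. Section 12.1 has a staff scientist trained in tissue collection and storage, and the documents do not say whether that person also gates. Masking to arm is therefore easier than masking to time point, although time point is the primary contrast. This stands, and it makes the locked gating template as important as the coded labels.

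Section 10 calls this a pilot study. That tempers the severity but does not argue against an inexpensive safeguard.

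**Conclusion.** The point holds in a limited form. The plan leaves laboratory masking unspecified, contradicts itself in one sentence on the platform for the primary ratio, and does not define the Treg gate explicitly. Since the primary test is a single-arm before/after comparison in 8 patients, nothing in the design absorbs a reading or platform difference between time points.

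As an illustration, assumed differential shifts of 1.2- to 1.5-fold would raise the false-positive rate from 5% to about 9% to 23%, at SD 0.808 and r = 0.5 with a two-sided test. These are not estimates of bias in this trial. A reader might infer that reader choice will produce the before/after change; the documents support only that it could, and only if reading differs by time point or an analysis is selected after the fact.

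The change should be made, but this is neither an arithmetic error nor a safety matter. It would not remove the separate difference between thoracoscopic biopsy and resection tissue.

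**What to change.** 1. **Platform.** Reconcile 7.3.1 with the primary endpoint definition and 8.1.1: both samples of a pair use CyTOF for the primary ratio, with flow cytometry as a sensitivity result only.
2. **Gate.** State the CD8 and Treg gates in Appendix C. Lock one gating template and apply it to all files before the code for arm and time point is broken.
3. **Coded reading.** Add to 5.4.1 and 7.3.1 that the existing coordinator puts coded labels on cytometry files and PD-L1 slides, so that gating and scoring are done without knowledge of arm and, as far as the specimens allow, of time point. Where the person gating also handled the tissue, say so and rely on the locked template.

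Cost: a short laboratory instruction and slightly slower access to individual results. No additional sample or assay is needed, and the sample size and stated power do not change.

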### **5.4.2 Methods for unblinding the study**

Not applicable.

## **5.5 Dosage and Administration**

MEDI4736 (15 mg/kg intravenously) or MEDI4736 (1500 mg intravenously) + tremelimumab (75 mg intravenously) will be administered once during the study.

Subjects under 30 kg will be treated with weight-based dosing for both MEDI4736 and Tremelimumab combination therapy. These patients are excluded from fixed based dosing to limit endotoxin exposure from the drug preparations.

## **5.6 Dose Escalation Decision Rules**

There will be no dose escalation in this study. Subjects randomized to either the MEDI4736 or MEDI4736 + tremelimumab will receive a single monotherapy or combination dose.

## **5.7 Definition of DLT**

Dose-limiting toxicities (DLTs) will not be evaluated during this study.

## **5.8      Toxicity Management**

### **5.8.1    MEDI4736**

For adverse events (AEs) that are considered at least partly due to administration of MEDI4736 the following dose adjustment guidance may be applied:

- Treat each of the toxicities with maximum supportive care (including holding the agent suspected of causing the toxicity where required).  
If the symptoms promptly resolve with supportive care, consideration should be given to continuing the same dose of MEDI4736 along with appropriate continuing supportive care.

In addition, there are certain circumstances in which MEDI4736 should be permanently discontinued.

Based on the mechanism of action of MEDI4736 leading to T-cell activation and proliferation, there is the possibility of observing immune related Adverse Events (irAEs) during the conduct of this study. Potential irAEs include immune-mediated enterocolitis, dermatitis, hepatitis, and endocrinopathies. Subjects should be monitored for signs and symptoms of irAEs. In the absence of an alternate etiology (e.g., infection or PD) signs or symptoms of enterocolitis, dermatitis, hepatitis, and endocrinopathy should be considered to be immune-related.

In addition, management guidelines for adverse events of special interest (AESIs) are detailed in Section 10.1.3. All toxicities will be graded according to NCI CTCAE v4.03.

